9.3.3. Vaccine management

The sponsor should provide the full amount of vaccine, including the alternate vaccine.

Test vaccine packaging must comply with the requirements of clinical trials.

Sponsor is responsible for transportation of the test vaccine to the research center, vaccine transportation temperature records (in accordance with the vaccine cold chain temperature) should be submitted along with the experimental vaccine together to investigators. The blind file, emergency blind file and inspection reports (qualified) should be submitted with the sponsor and manager in research center.

Special area should be used to store and lock the test vaccine to get rid of unauthorized persons. Vaccine is forbidden to inject other ones except participants.

The temperature of the monitoring instrument, transport and storage of the vaccine should be daily monitored (am and pm manually). Once the temperature deviation happened, as the temperature beyond the provisions of the range of 2-8, the investigators and sponsors should be immediately informed, and the “cold chain damage report form” should be filled in, too. The temperature-deviated vaccine should be identified, placed separately and suspended. Continual usage of vaccines must be written approved by Biotechnology Institute of Academy of Military Medical Sciences/Tianjin CanSino Biotechnology Inc. Vaccine out of requirements should be on-site sequestration.

The test vaccine should be stored in a refrigerator or freezer and cold chain equipment is equipped with a thermometer with the vaccine administrator records temperature every 15 minutes.

Vaccine administrators release the test vaccine to the vaccination staff according to number of participants and vaccine. The left test vaccine packing should be recycled after inoculation and detailed records of test vaccine and recycling packaging are needed

At the end of vaccination, vaccine and package of the vaccine will be checked and recycling stored by administrator. At the end of the study, the researchers will check all the remaining vaccine and package and deliver them back to sponsors.

At any time, the total number of vaccines, unused or damaged vaccines must be consistent with the applicants provided, otherwise, description is needed to be provided by investigator.

9.3.4. Alternate vaccine

500 person-dose of blind packing experimental vaccine should be provided by sponsors. Another 30 person-dose of experimental vaccine A, experimental vaccine B and placebo, respectively should be provided in case of vaccine damage or other unusable situation. If vaccine is damaged, the non-blind physicians could replace vaccine according to the corresponding category of participant. Although there's no need immediately noticing the sponsor in this case (except cold chain accident), the investigator should have vaccine damage and replacement record in details.

9.3.5. Combined medication/vaccine

When the medical events happen during the study period, the participant are allowed to carry out the appropriate medical treatment, but the medical treatment should be recorded in time.

Other vaccination is not recommended except for emergency during the research period, such as rabies vaccine, tetanus vaccine, or other emergent vaccination need. Any vaccine used is required to be recorded during the study period.

9.4. Safety follow-up

9.4.1. Methods of safety observation

After vaccination, each participant will be asked to stay at study site for at least 60 mins safety surveillance. Doctors will monitor the general safety condition of the participants and teach them to observe any adverse reactions or events on the diary card. Doctors will teach them how to use a digital thermometer to measure the temperature. If there is no significant adverse reactions, participants will be allowed to go home and report auxiliary temperature and any adverse events (AEs) for seven consecutive days. Each participant will get a digital thermometer, a measure ruler and a cell phone before he or she leave the site for reaction measurement and report.

During the first 7 days after vaccination, several trained staffs will collect the safety data from participants daily by phone or home visit. These trained staffs will record the temperature and any adverse event reported by participants on the Diary Card. If the symptom of reaction is severe and needs medical intervention, the trained staffs must instruct the participants to seek the treatment in community clinics, and record the treatment on the Diary Card.

From day 8 to the end of the study, no need to collect the adverse event actively. But once a serious adverse event is reported from subject, the staff will immediately inform the principal investigator by telephone. And assist with the serious adverse investigation.

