
Scheduled site visits
	
Visit 0 (day -1): informed consent, and demographic information collecting
 
Visit 1 (day0): screening, physical examination, blood sample taking for HIV test, haematology and clinical chemistry test, and baseline antibody detection; pregnancy test. followed by immunization/administration of vaccine
 
Visit 2 (day 14, ± 2 days): assessment of safety, blood sample taking for post-vaccination antibody detection.
 
Visit 3 (day 28, ± 3 days): assessment of safety, blood sample taking for post-vaccination antibody detection.
 
Visit 4 (day 168, ± 10 days): assessment of safety, blood sample taking for HIV test and post-vaccination antibody detection.

Criteria for pausing or early termination
	
DSMB will review the reported safety data in the participants after vaccination. During the study period, if an increase of risk for participants is noticed, the DSMB should promptly inform the principal investigator and sponsors. Sponsors, investigators and DSMB will have a panel meeting, and then DSMB will make final decision to pause or call an early termination of the study. Administration of study injections and new enrollments will be paused, if:
 
 - One serious adverse event may be associated with vaccination, or - Incidence of new HIV infection post-vaccination reported in one (1) participant during 6 months after vaccination. 
The study may come to an early termination, if:
 
 - One fatal serious adverse event definitely associated to vaccination, or - Incidence of new HIV infection reported in 1% (5 participants) during the 6 months post-vaccination, or - Required by sponsor, or - Required by regulatory authority, or - Required by institutional review board (IRB).

Inclusion Criteria
	
 - Aged between 18 and 50 years - Able to understand the content of informed consent and signed the informed consent

	
- Able and willing to complete all the secluded study process during the whole study follow-up period (about 6 months).- Negative in HIV diagnostic blood test on the day of enrollment- Axillary temperature $\leq 37.0^{\circ}$ C on the day of enrollment- Non-pregnant females with a negative result in the urine pregnancy test on day of enrollment- General good health as established by medical history and physical examination.

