7.2.2. Secondary endpoints

7.2.2.1. Safety

- Occurrence of unsolicited adverse reactions within 28 days after vaccination.
- Occurrence of serious adverse reaction during the whole follow-up period (6 months).
- Post-vaccination Rate of infected with HIV.

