7.3. Study Procedures

From beginning to the end of the study, there are 5 times visits of participants. The visit time, window period and visit content are shown in table 7-3-1 and 7-3-2.

Table.7-3-1 Visit plan for recombinant Ebola virus vaccine (Ad5-EBOV)

Visit	Visit time	Time window
Visit 0 (V0)	One day before the vaccination	—
Visit 1 (V1)	Vaccination at Day 0	—
Visit 2 (V2)	Day 14 after vaccination	±2 days
Visit 3 (V3)	Day 28 after vaccination	±3 days
Visit 4 (V4)	Day 168 (Month 6) after vaccination	±10 days

Table.7-3-2 Visit content and schedule for recombinant Ebola virus vaccine (Ad5-EBOV)

Content	V0	V1	V2	V3	V4
	Day	Day	Day	Day	Day
	-1	0	14	28	168
1 Collecting demographic information	☆				
2 HIV informed consent	☆				
3 Study Informed consent	☆				
4 Physical examination					

	Height, weight measurement		☆			
	Urine pregnancy tests (female)		☆			
	HIV antibody screening		☆			☆
5	Axillary temperature measurement		☆			
6	Inclusion and exclusion criteria for screening		☆			
7	Allocation of vaccine ID		☆			
8	Record on the Visit Record Form		☆			
9	Blood collection *:					
	Haematology and clinical chemistry tests ^		☆			
	Detection of anti-Zaire Ebola virus envelope glycoprotein antibody		☆	☆	☆	☆
	Detection of neutralizing antibodies to recombinant replication defective type 5 adenovirus		☆	☆	☆	☆
10	Vaccination		☆			
11	Observation for 60 minutes post-vaccination		☆			
12	Instruction on observation of solicited /unsolicited symptoms		☆			
13	Record of solicited / unsolicited symptoms post-vaccination		☆	☆	☆	
14	Report serious adverse events		☆	☆	☆	☆
15	Return of diary card		Return by safety follow-up staffs at day 8			

*Participants will be asked to donate 8ml blood (uncoagulation: 3ml, coagulation: 5ml) at the first visit, and 5 ml blood sample at the later visits. A total of 23 ml blood will be donated for each participant.

^ The toxicity grading panel for the haematology and clinical chemistry tests are provided in Appendix 13.

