8.5. Termination of study

8.5.1. Completed safety observation

Safety of 28 days after immunization and the SAE reports in entire study period are completed.

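### Section 9.4.1 ends active adverse event collection at day 8, which contradicts the 28-day unsolicited-reaction endpoint and the symptom recording scheduled at days 14 and 28

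*Protocol*

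**What the plan says.** Section 9.4.1 describes two phases of safety follow-up. In the first, "During the first 7 days after vaccination, several trained staffs will collect the safety data from participants daily by phone or home visit", and staff write what they hear on the diary card. The second phase is governed by one sentence: "From day 8 to the end of the study, no need to collect the adverse event actively". The only instruction after it concerns serious events: "But once a serious adverse event is reported from subject, the staff will immediately inform the principal investigator by telephone". The last row of Table 7-3-2 has the diary card collected ("Return by safety follow-up staffs at day 8"), while section 9.4.7 names that card as the place to record clinically meaningful events after vaccination.

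Other parts of the protocol look further ahead. Section 7.2.2.1 lists as a secondary safety endpoint: "Occurrence of unsolicited adverse reactions within 28 days after vaccination". Section 8.5.1 defines when safety observation is complete: "Safety of 28 days after immunization and the SAE reports in entire study period are completed". Item 13 of Table 7-3-2, "Record of solicited / unsolicited symptoms post-vaccination", is marked at V1, V2 and V3. The visit list in the Protocol Summary gives "Visit 2 (day 14, ± 2 days): assessment of safety, blood sample taking for post-vaccination antibody detection", and also lists a safety assessment at Visit 3 (day 28, ±3 days).

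**The concern.** The section that tells staff how to observe safety contradicts the endpoint list and the visit schedule on whether non-serious events are sought between day 8 and day 28. Someone working from 9.4.1 would stop asking after the first week. Someone working from Table 7-3-2 would ask at two further visits. The 28-day rate would then depend on which part of the protocol was followed, and it would join a week of daily staff contact to three weeks of undefined collection.

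What is at stake is one named secondary endpoint. The statistical analysis plan cannot repair a gap here, because an event that was never asked about leaves no record to analyse. Any error runs toward apparent safety, in a trial meant to help choose a dose for phase III.

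**Working it through.** **Inputs**

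- Endpoint window: 28 days (section 7.2.2.1; Protocol Summary, Endpoints).
- Daily staff contact: first 7 days (section 9.4.1).
- Diary card returned: day 8 (Table 7-3-2).
- V2: day 14 ±2, so days 12 to 16. V3: day 28 ±3, so days 25 to 31 (Table 7-3-1).
- Symptom recording marked at V1, V2 and V3, not at V4 (Table 7-3-2, item 13).

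The protocol gives no figure for how completely late events are captured, so there is no stated result to reproduce.

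**Step 1. Share of the window without daily outreach.** (28 − 7)/28 = 21/28 = 75.0%. Counting day 0 as a day of its own gives 21/29 = 72.4%. This is a share of time without daily contact. It is neither the share of time without any contact nor the share of events.

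**Step 2. The two readings.**

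- *Section 9.4.1 taken literally.* From day 8 nobody asks, the card has gone, and only serious events have a stated route. Non-serious events reach the database only if the participant volunteers them.
- *Visit schedule governs.* Participants are seen at V2 and V3, but recall is unaided by a diary. It covers 12 − 7 = 5 to 16 − 7 = 9 days up to V2, then 25 − 16 = 9 to 31 − 12 = 19 days from V2 to V3. If V3 takes place on day 25, days 26 to 28 (28 − 25 = 3 days) fall after the last enquiry.

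Collection is less intensive than in week 1 on both readings. Only the first leaves non-serious events unsought.

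**Step 3. Direction of the error.** For arm k, let e_k be the proportion with an unsolicited reaction by day 7, and l_k the proportion whose first one occurs in days 8 to 28. Let s be the probability that such a late reaction is captured, assumed equal across arms and without false reports.

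- Observed rate = e_k + s·l_k, against a true rate of e_k + l_k. The shortfall is (1 − s)·l_k.
- Observed difference = (e_1 − e_0) + s·(l_1 − l_0). The early part is untouched and the late part is multiplied by s.

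Section 9.7.4.1 counts individuals and counts a repeated event once, so a participant already counted in week 1 is not lost through a later miss.

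**Step 4. Range under assumptions.** Let f be the share of affected participants whose reaction arises only after day 7. Overall capture = (1 − f) + f·s. The documents give neither f nor s. The values below are assumptions.

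| f | s = 0 | s = 0.5 | s = 0.8 | s = 1 |
|---|---|---|---|---|
| 0.25 | 75% | 87.5% | 95% | 100% |
| 0.50 | 50% | 75% | 90% | 100% |
| 0.75 | 25% | 62.5% | 85% | 100% |

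Overall capture runs from 25% to 100%, and complete capture is not excluded.

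**The case against.** The best defence is that the sentence in 9.4.1 follows directly on the account of daily phone calls and home visits, and may mean only that this outreach stops. On that reading V2 and V3 do the collecting, as the table and visit list provide, and the wording of the question may sit in the CRF or procedures that are not shown. This reading is possible and it limits the finding. It does not remove it: the sentence carries no such limit, it is followed by a route for serious events alone, and the named recording tool is withdrawn at the same point.

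Several stronger readings are tempting and are not supported:

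- *The endpoint will be under-counted for three quarters of its window.* The scheduled enquiries at days 14 and 28 make under-counting conditional on 9.4.1 being followed literally.
- *All safety rates are biased down.* The primary safety endpoint covers solicited reactions within 7 days, which daily contact spans. Serious events have their own reporting route throughout (Table 7-3-2, item 14; section 9.4.5).
- *Illiteracy makes late reporting unreliable.* The amendment history gives illiteracy as a reason why some participants could not complete the diary card themselves. It does not prevent an oral report at a visit or on the phone that each participant receives.
- *Late rates are understated by 40% to 70%.* That follows from assuming that 30% to 60% of late events are captured. The documents give no such figure, it presupposes purely spontaneous reporting, and it describes the late part of the window rather than the 28-day endpoint.

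It is also fair to say that the safety analysis is mainly descriptive (section 9.7.5.1). Blinding is planned to hold until the day-28 data are locked (sections 9.2.2 and 9.2.3), so misses should be largely non-differential. That makes a spurious difference between arms unlikely, but it does not prevent lower rates or a weaker comparison.

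**Conclusion.** The concern holds as an internal contradiction. Section 9.4.1 does not fit the 28-day unsolicited-reaction endpoint, the completion definition in 8.5.1, or the collection scheduled at V2 and V3. If it is followed literally, non-serious unsolicited events over 21 of the 28 days rest on spontaneous report and may be under-counted. Rates for this one endpoint would then be too low. With equal capture across arms, the late contribution to between-arm differences would shrink in proportion to capture.

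The size cannot be computed from the documents. The 25% to 100% range for overall capture rests wholly on assumed shares of late reactions and assumed capture, and shows only how wide the uncertainty is.

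**What to change.** Reconcile the passages by replacing the sentence in 9.4.1 with a rule to this effect: daily phone or home contact ends after day 7. At V2 and at V3 every participant is asked the same non-leading question about any event since the last contact. Each event is entered on the CRF with onset date, severity and causality. Where V3 falls before day 28, the enquiry is completed through day 28, for example by phone.

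Section 9.4.7 should name the CRF as the recording tool once the diary card has been returned. Causality has to be recorded because the endpoint counts reactions, whereas the question asks about events.

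The cost is a few minutes at visits that already take place, one CRF page, and a short call for participants whose V3 is early. No visit is added.

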9.4.2. Safety observation and grade of adverse reaction/event

9.4.2.1. Definition of adverse event and serious adverse event

An adverse event (AE) is any untoward medical occurrence in a participant administered an

investigational product and which does not necessarily have a causal relationship with this treatment. A serious adverse event/reaction (SAE) is occurrence of any untoward medical during the whole study period that:

- Results in death.
- Is life-threatening (an event in which the participant is at risk of death at the time of the event; it does not refer to an event which hypothetically might have caused death if it was more severe).
- Results in persistent or significant disability/incapacity.
- Requires hospitalization or prolongation of an existing hospitalization.
- Is a congenital anomaly/birth defect.

In addition, medical and scientific judgment will be exercised in deciding whether other conditions will also be considered serious, such as important medical events that may not be immediately life-threatening or result in death or hospitalization but may jeopardize the participant's safety or may require intervention to prevent one of the other outcomes listed in the definition above. These will also be considered serious. Examples of such events are intensive treatment in an emergency room or at home for allergic bronchospasm; blood dyscrasias or convulsions that do not result in hospitalization; or development of drug dependency or drug abuse.

9.4.2.2. Grading for adverse events

All adverse events will be graded according to “The standard guidelines for adverse reactions grading of vaccine clinical trials” issued by China state Food and Drug Administration (SFDA). The presence of solicited and unsolicited adverse events and any serious adverse events will be described in terms of the incidence, intensity and relation to vaccination. The incidence of adverse events will be based on the most severe response, and expressed in terms of the number and proportion of individuals who had adverse events in each group.

Injection site

Pain (at the injection site)

Grade 1(mild)= Mild pain when the injection site was touched

Grade 2(moderate)= Moderate pain when the injection site was touched

Grade 3(severe) = Severe pain, refuse to be touched at the injection site

Grade 4(potentially life threatening) = Need emergency treatment or hospitalization

Induration (at the injection site)

Grade 1 (mild) = Diameter : <15mm

Grade 2 (moderate) = Diameter :15~30mm

Grade 3(severe)= diameter >30 mm- ≤ 50 mm

Grade 4 (potentially life threatening)= Gangrene

Redness (at the injection site)

Grade 1 (mild) = Diameter : <15mm

Grade 2 (moderate) = Diameter : 15~30mm

Grade 3(severe)= Diameter : >30mm

Grade 4(potentially life threatening)= Gangrene

Swelling (at the injection site)

Grade 1 (mild) = Diameter : <15mm, with no limited movement

Grade 2 (moderate) = Diameter :15~30mm; with limited movement

Grade 3(severe)= Diameter :>30mm; with severely limited movement

Grade 4(potentially life threatening) = Gangrene

Rash (at the injection site)

Grade 1 (mild) = Diameter : <15mm

Grade 2 (moderate) = Diameter :15~30mm

Grade 3(severe)= Diameter :>30mm

Itch (at the injection site)

Grade 1 (mild) = Mild itch at injection site

Grade 2 (moderate) = Moderate itch on injected arm

Grade 3(severe)= Severe itch all over the body

Systemic reactions

Fever (axillary temperature)

Grade 1(mild) = $\geq 37.1^{\circ}\text{C} \leq 37.5^{\circ}\text{C}$

Grade 2(moderate) = $\geq 37.6^{\circ}\text{C} \leq 39.0^{\circ}\text{C}$

Grade 3(severe) =>39.0°C

Allergic reactions

Grade 1(mild) = Itch without rash

Grade 2(moderate) = Localized urticaria

Grade 3(severe) = Generalized/extensive urticaria, angioedema

Grade 4(potentially life threatening) = Severe allergic reactions

Headache

Grade 1(mild) = Mild, with no interfere with daily activities

Grade 2(moderate) = Moderate, with a mild impact on daily activities

Grade 3(severe) = s Severe, with a significant impact on daily activities, need a treatment

Grade 4(potentially life threatening) = Stubborn headache, need an emergency treatment or hospitalization

Fatigue

Grade 1(mild) = Mild, with no interfere with daily activities, last no more than 48 hours

Grade 2(moderate) = Moderate, with a mild impact on daily activities, last over 48 hours

Grade 3 (severe) = Severe, with a significant impact on daily activities, can't work

Grade 4 (potentially life threatening) = Unable to do anything, need an emergency treatment or hospitalization

Nausea /Vomiting:

Grade 1(mild) = 1~2 episodes per 24 hours, with no interfere with eating and drinking

Grade 2(moderate) = 2~5 episodes per 24 hours, with a mild impact on eating and drinking

Grade 3(severe) = >6 episodes per 24 hours, with a significant impact on eating and drinking, need a treatment

Grade 4(potentially life threatening) = Need an emergency treatment or hospitalization

Diarrhea:

Grade 1(mild) = Mild, 2~3 loose stools per day or mild diarrhea last <1 week

Grade 2(moderate) = Moderate, 4~5 loose stools per day, diarrhea last >1 week

Grade 3(severe) = Severe, >6 loose stools per day, or bloody stool, electrolyte imbalances, need a treatment

Grade 4(potentially life threatening) = Need an emergency treatment or hospitalization

Muscle pain

Grade 1(mild) = Mild, with no interfere with daily activities

Grade 2(moderate) = Moderate, with a mild impact on daily activities

Grade 3(severe) = Severe, with a significant impact on daily activities, need a treatment

Grade 4(potentially life threatening) = Need an emergency treatment or hospitalization

Joint pain

Grade 1(mild) = Mild, with no interfere with daily activities

Grade 2(moderate) = Moderate, with a mild impact on daily activities

Grade 3(severe) = Severe, with a significant impact on daily activities, need a treatment

Throat pain

Grade 1(mild) = Mild, with no interfere with daily activities

Grade 2(moderate) = Moderate, with a mild impact on daily activities

Grade 3(severe) = Severe, with a significant impact on daily activities, need a treatment

Cough

Grade 1(mild) = Transient, need no treatment

Grade 2(moderate) = Persistent cough, resolved after treatment

Grade 3(severe) = Severe cough, not resolved after treatment

Grade 4(potentially life threatening) = Need an emergency treatment or hospitalization

The general grading principles for other adverse reactions (the clinical abnormalities that were not involved in the above classification):

Grade1 (mild) = Mild, with no interfere with daily activities

Grade 2 (moderate) = Moderate, with a mild impact on daily activities

Grade 3 (severe) = Severe, with a significant impact on daily activities, need a treatment

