9.4.7. Record of safety observation

Any clinically meaningful adverse event occurred after vaccination should be recorded in the diary card. Verification and medical visits by investigator respond to adverse events are required, such as investigation of medical history, physical examination and necessary laboratory examination (if required). Participants should receive appropriate medical treatment until the adverse event decline completed with complete records.

The record of adverse events should include the following:

- Description of adverse events
- Start and end time of adverse events
- Severity (grade)
- Relationship with vaccination
- Laboratory findings
- Treatment measures
- Outcome

If there are allergies, SAE, or a level 3 adverse events or above happening in safety observation period, medical treatment should be provided until symptoms disappeared or stabilization of symptoms. Record the details of visit exactly.

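### The printed severity bands for vomiting, diarrhoea and induration are not exhaustive and mutually exclusive, so a few values fit two grades or none

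*Protocol*

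**What the plan says.** Protocol 9.4.2.2 says that all adverse events are graded by a named guideline of the Chinese regulator. It then prints its own grade definitions, reaction by reaction. For nausea and vomiting:

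- Grade 1: "Grade 1(mild) = 1~2 episodes per 24 hours, with no interfere with eating and drinking"
- Grade 2: "Grade 2(moderate) = 2~5 episodes per 24 hours, with a mild impact on eating and drinking"
- Grade 3 starts: "Grade 3(severe) = >6 episodes per 24 hours"

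Diarrhoea grade 1 is two to three loose stools a day, or mild diarrhoea for under a week. Grade 2 is "4~5 loose stools per day, diarrhea last >1 week". Grade 3 is "Severe, >6 loose stools per day, or bloody stool", with further clinical features. Grade 4 for both reactions is a need for emergency treatment or hospitalization.

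Induration is grade 1 below 15 mm and grade 2 from 15 to 30 mm. The third band is "Grade 3(severe)= diameter >30 mm- ≤ 50 mm", and grade 4 is gangrene only.

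The same section commits to describing intensity as well as incidence and relation to vaccination: "The incidence of adverse events will be based on the most severe response". Section 9.7.4.1 assigns the worst severity when a participant has the same event more than once. Section 9.4.7 attaches continued treatment and detailed recording to "a level 3 adverse events or above happening in safety observation period", and section 12.3.2 also refers to grade 3 or above.

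**The concern.** A severity scale used to summarise each participant by worst grade has to place every observable value in exactly one grade. Three of the printed scales do not. This is not detail left for an analysis plan: the thresholds are stated, and the fault lies in what they state. Grading is also done during data collection, so a value sorted differently by different staff may be hard to recover at analysis.

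The trial is meant to choose a dose for phase III (section 1), and section 5.4.1 reports a dose-response for local reactions in phase I. The intensity of local reactions is therefore relevant to comparing the two doses, even though it is not the primary endpoint. Participants receive a ruler (9.4.1), so lesion size will be measured.

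**Working it through.** No power or error-rate calculation applies, and the plan gives no figure to reproduce. The check takes each band in 9.4.2.2 as an interval exactly as printed, runs through the possible values, and counts how many grades each value matches.

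| Scale | Grade 1 | Grade 2 | Grade 3 | Fits two grades | Fits none |
|---|---|---|---|---|---|
| Vomiting, episodes per 24 h (1 to 10 checked) | 1–2 | 2–5 | >6 | 2 | 6 |
| Diarrhoea, loose stools per day (2 to 10 checked) | 2–3 | 4–5 | >6 | none | 6 |
| Induration, mm (1 to 80 checked) | <15 | 15–30 | >30 to ≤50 | none | every value from 51 to 80 |
| Redness, swelling, rash, mm (1 to 80 checked) | <15 | 15–30 | >30 | none | none |
| Fever, °C in 0.1 steps from 37.1 | 37.1–37.5 | 37.6–39.0 | >39.0 | none | none |

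The last two rows are controls. The same strict reading gives exactly one grade for every value there, so the faults are specific to the first three scales.

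Next, can the rest of the text settle the faulty values?

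- **Two vomiting episodes.** Grade 1 goes with no interference with eating and drinking, grade 2 with a mild impact. That wording can often separate the grades. No rule says which criterion prevails when count and impact disagree.
- **Six vomiting episodes.** The count lies above grade 2 and below grade 3. The functional wording is joined to a count in each band, so it does not by itself assign a grade. Grade 4 has no count and catches only cases needing emergency treatment or hospitalization.
- **Six loose stools a day.** Blood in the stool, or the other grade 3 or grade 4 features, can place a case. Six non-bloody stools without such features lie in no count band.
- **Induration above 50 mm.** Grade 4 is gangrene and carries no diameter. The induration bands have no functional wording, so nothing else in the scale can place the value.
- **General grading principles at the end of 9.4.2.2.** These are confined to abnormalities outside the listed classification. Vomiting, diarrhoea and induration are all listed, so the principles do not fill the gaps.
- **Worst-severity rules in 9.4.2.2 and 9.7.4.1.** These choose among grades already assigned. They do not say how to grade a single event that matches two bands or none.

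**The case against.** The best case on the other side is that the consequences are small, and most of it stands.

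- **Endpoint and pausing rules.** The primary safety endpoint in 7.2.1.1 is occurrence within 7 days, and every boundary case still counts as an occurrence. The pausing and termination rules in 7.5 rest on serious adverse events, HIV infection and requests by the sponsor or authorities, not on grade 3.
- **Severe gastrointestinal events.** A reader might infer that the worst of these escape the grade 3 count. The bands do not support that. Seven or more episodes or stools meet the grade 3 count, bloody stool is listed in grade 3, and a need for emergency treatment or hospitalization is grade 4. Only a count of exactly six is stranded. Induration is the one scale whose largest values have no grade.
- **Care.** A reader might also infer that ungraded participants would go without care. Sections 9.4.7 and 9.4.8 require appropriate treatment for adverse events generally, and 9.4.1 refers severe symptoms for treatment without a numeric grade.
- **Diarrhoea lasting exactly one week.** This too falls between two bands, but it rarely matters. The daily count settles most cases, the solicited window is 7 days, and active collection stops from day 8.
- **Rarity.** Section 5.4.1 reports only grade 1 local responses in the Chinese phase I trial, which included the same high dose. Large indurations may therefore be uncommon, although that trial had only 120 participants across all groups.
- **The cited guideline.** It may contain clean bands. It is not available here, and the protocol prints its own list. If the two differ, the protocol holds two rules; if they agree, the gaps remain.

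**Conclusion.** The point holds in limited form. As printed, one vomiting count (two) fits two grades. One vomiting count (six) and one stool count (six, non-bloody and without other grade 3 or 4 features) fit no count band. An open-ended range of induration (above 50 mm without gangrene) has no grade, whereas the neighbouring local reactions have no such cap.

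The effect is confined to the worst-grade intensity description and to the grade 3 or above classification used in 9.4.7 and 12.3.2. The documents give no expected frequencies for vomiting, diarrhoea or induration, so the number of participants affected cannot be stated. The conclusion assumes that site staff grade from the printed list, and that the listed symptoms are the solicited ones; the protocol has no separate list of solicited reactions. Neither the diary card nor the guideline was available to check.

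**What to change.** Revise 9.4.2.2 in three respects.

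1. Reconcile the vomiting, diarrhoea and induration bands with each other and with the cited grading guideline, so that every count and diameter falls in exactly one grade. The values to settle are two and six vomiting episodes, six loose stools a day, and induration above 50 mm without gangrene.
2. State which criterion prevails when the count and the functional impact point to different grades.
3. Print the same bands on the diary card and CRF before the first reaction is graded.

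The documents do not show which cut-off is right; that is for the sponsor to settle. The cost is a few words in the protocol and matching forms, with no extra participants, visits or data.
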